6.8.1.2.5 Tear Break-Up Time (TBUT)

The TBUT will be done at each visit in each eye. The value at Day 1 will be the baseline value.

The tear break-up time will be measured three times during the first minute after the instillation of one drop of fluorescein. The TBUT value analysed will be the sum of the three measurements.

6.8.1.2.6 *Conjunctival hyperaemia using Mac Monnies photographic scale*

The conjunctival hyperaemia will be assessed using the Mac Monnies photographic scale in each eye ([Figure 9](#)). The value at Day 1 will be the baseline value.

Figure 9 **Mac Monnies photographic scale**

6.8.1.2.7 *Ocular symptoms*

Patient will be asked:

“How do you judge the severity of your following ocular symptoms **WITHIN THE LAST 48 HOURS?**”

*« Comment jugez-vous la sévérité de vos symptômes oculaires suivants ressentis **DANS LES DERNIERES 48 HEURES?** »*

The severity of the following ocular symptoms (global evaluation for both eyes) will be assessed at each visit: **burning/irritation, stinging/eye pain, itching, eye dryness feeling, foreign body sensation, light sensitivity and fluctuating blurred vision** as follows:

- (0) = Absent;
- (1) = Mild, Present but not disturbing;
- (2) = Moderate, Disturbing, but not limiting daily activities;
- (3) = Severe, Very distressing and interfering with daily activities.

6.8.1.2.8 *Ocular symptoms upon instillation:*

Patient will be asked: “Have you felt any unusual sensation upon instillation since the last visit?”

« Avez-vous ressenti une gêne/sensation oculaire inhabituelle à l’instillation depuis la dernière visite ?»

If the answer is yes, a table regrouping the functional ocular signs will have to be completed. Ocular symptoms upon instillation at Day 8 (optional), Day 35 and Day 84: Burning/irritation, stinging/eye pain, itching, eye dryness feeling, foreign body sensation, light sensitivity and other symptoms will be graded by the subject according to the following severity scale and with their duration:

- (0) = Absent;

- (1) = Mild, Present but not disturbing;
- (2) = Moderate, Disturbing, but not limiting daily activities;
- (3) = Severe, Very distressing and limiting with daily activities.

6.8.1.2.9 *Performance assessment by the investigator*

The evaluation of the IMD performance will be assessed by the investigator, using the following rating scale:

- Very satisfactory;
- Satisfactory;
- Not very satisfactory;
- Unsatisfactory.

6.8.2 **Safety measures**

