3.2 Safety assessments

Other evaluation parameters are:

- Ocular unusual sensation upon instillation at Day 8, Day 35 and Day 84:

Burning/irritation, stinging/eye pain, itching, eye dryness feeling, foreign body sensation, light sensitivity and other symptoms will be graded by the subject according to the following severity scale and with their duration: (0 = Absent; 1 = Mild, Present but not disturbing; 2 = Moderate, Disturbing, but not limiting daily activities; 3 = Severe, Very distressing and interfering with daily activities);

- Far best-corrected visual acuity (in logMAR) at Day 84;
- Tolerance assessment by the patient and the investigator (Unsatisfactory, Not very satisfactory, Satisfactory, Very satisfactory) at Day 35 and Day 84 ;
- Ocular and systemic adverse events (AE/SAE).

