Severity/Intensity of Dry Eye Symptoms at each visit	
If CESEV="ABSENT" Then CESEVn=0
 
If CESEV="MILD, PRESENT BUT NOT DISTURBING" Then CESEVn=1
 
If CESEV="MODERATE, DISTURBING, BUT NOT LIMITING DAILY ACTIVITIES" Then CESEVn=2
 
If CESEV="SEVERE, VERY DISTRESSING AND INTERFERING WITH DAILY ACTIVITIES" Then CESEVn=3
	Severity / Intensity (n)	0="Absent" 1="Mild" 2="Moderate" 3="Severe"
Dry Eye Symptoms	
If, for the visit i patient does not have all symptoms, missing symptoms will be created with CESEVn=0
 
Only for CECAT="Ocular Symptoms"
	Severity / Intensity (n)	0="Absent" 1="Mild" 2="Moderate" 3="Severe"
Dry eye symptoms at each visit	
SCORE_DES=Sum(CESEVn) Where CECAT=Ocular Symptoms
 
Only for the 7 predefined dry eye symptoms and if the 7 predefined dry eye symptoms are not missing
	Total score of Dry Eye symptoms	Numeric (8.1)

The 7 predefined dry eye symptoms are: Burning/Irritation, Stinging/Eye pain, Itching, Eye dryness feeling, Foreign body sensation, Light sensitivity and Fluctuating blurred vision			
Total score of Dry Eye symptoms at Days 1, 8, 35 and 84	BS SCORE_DES= Total score of Dry Eye Symptoms at D1 (SCORE_DES) EVOL_SCORE_DESi=(SCORE_DESi– BSSCORE_DES) i=Days 8, 35 and 84 (data are in line in the table)	Change from baseline in total score of dry eye symptoms on Day i	Numeric (8.1)
Change from baseline in total score of dry eye symptoms on Day 8 (i.e. Days 35 and 84)	If .Z<EVOL_SCORE_DESi<0 Then EVOL_SCORE_DESCi=1 If EVOL_SCORE_DESi=0 Then EVOL_SCORE_DESCi=2 EVOL_SCORE_DESi>0 Then EVOL_SCORE_DESCi=3 i=Days 8, 35 and 84 (data are in line in the table)	Evolution Dry Eye symptom on Day i	1="Improvement" 2="Stable" 3="Worsening"
Symptoms upon instillation	If, for the visit i patient does not have symptoms upon instillation, 6 lines will be created for the 6 predefined symptoms, with CESEVn=0 Only for CECAT="Ocular Symptoms Upon Instillation"	Severity / Intensity (n)	0="Absent" 1="Mild" 2="Moderate" 3="Severe"
Symptoms upon instillation	SCORE_UPON= Sum(CESEVn) Where CECAT= Ocular Symptoms Upon Instillation Only for the 6 predefined dry eye symptoms and if the 6 predefined dry eye symptoms are not missing	Total score of unusual sensation UPON INSTILLATION	Numeric (8.1)
The 6 predefined dry eye symptoms are: Burning/Irritation, Stinging/Eye pain, Itching, Eye dryness feeling, Foreign body sensation and Fluctuating blurred vision			

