6.8.1 Safety endpoints

- Descriptive tables will be produced by frequency and percentage, for the presence of each ocular unusual sensation UPON INSTILLATION at least one time during the study (for each ocular unusual sensation UPON INSTILLATION)
- Descriptive tables will be produced by frequency and percentage, for each ocular unusual sensation UPON INSTILLATION and by mean (SD) for the total score for the 6 predefined symptoms at Day 8, Day 35 and Day 84.
- The total score for the 6 predefined symptoms will be compared between treatment groups using Student T-test, if data have normal distribution. If it is not the case, Mann-Whitney Wilcoxon test will be used.

Note: For the analysis of ocular unusual sensation UPON INSTILLATION, usual severity, usual duration and frequency will be set to 0 if the patient felt no ocular unusual sensation upon instillation or if the severity is equal to 0 (absent).

- Far best-corrected visual acuity (in logMAR) at Selection visit, Day 35 and Day 84 will be described by mean (SD) for the worst eye and for the contralateral eye. The frequency distribution will be also presented in /10 (1/10, 2/10 to 10/10, >10/10);
- Tolerance assessment by the investigator and by the patient at Day 35 and Day 84 will be described in 4 classes and in 2 classes (Very satisfactory or satisfactory, not very satisfactory or unsatisfactory). The treatment groups for 4 classes description will be compared using a Cochran-Mantel-Haenszel (CMH) test.

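### The instillation-sensation total is 0 for every symptom-free patient but has no fill rule for patients with some sensations, and its six items are not the six collected, so symptomatic patients may lose their score

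*SAP*

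**What the plan says.** **Collection.** Protocol 6.8.1.2.8 has the patient first asked whether any unusual sensation was felt on instillation since the last visit. "If the answer is yes, a table regrouping the functional ocular signs will have to be completed". Grading is from 0 (absent) to 3. The list in SAP 3.2, which matches Protocol 6.3.3 and 6.8.1.2.8, ends: "foreign body sensation, light sensitivity and other symptoms will be graded by the subject according to the following severity scale".

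**Derivation (SAP 3.3, SCORE_UPON).** Zeros are supplied in one situation: "If, for the visit i patient does not have symptoms upon instillation, 6 lines will be created for the 6 predefined symptoms, with CESEVn=0". The total is then the sum of the severities, subject to a condition: "Only for the 6 predefined dry eye symptoms and if the 6 predefined dry eye symptoms are not missing". The items are defined as follows: "The 6 predefined dry eye symptoms are: Burning/Irritation, Stinging/Eye pain, Itching, Eye dryness feeling, Foreign body sensation and Fluctuating blurred vision".

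**The neighbouring dry-eye score (SAP 3.3, SCORE_DES).** Here zeros are supplied item by item: "If, for the visit i patient does not have all symptoms, missing symptoms will be created with CESEVn=0". That rule is restricted to the ocular-symptoms category, so it does not reach the instillation items.

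**Analysis (SAP 6.8.1).** "The total score for the 6 predefined symptoms will be compared between treatment groups using Student T-test, if data have normal distribution"; otherwise a Mann-Whitney Wilcoxon test is used. A note deals with how severe, how long and how frequent each sensation usually was; these values "will be set to 0 if the patient felt no ocular unusual sensation upon instillation or if the severity is equal to 0 (absent". Apart from LOCF for the primary endpoint in the FAS and partial treatment dates, SAP 5.3 leaves missing data unreplaced.

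**The concern.** Whether a patient has a total can depend on what the patient felt. Someone with no sensation always scores 0. Someone with one to five of the six sensations, or only a sensation recorded under other symptoms, scores only if the remaining items exist as stored lines, and the SAP has no rule that creates them. The mismatch in the item list makes this worse, because one of the six required items is not named among those collected.

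At stake is the comparison of the total score in Table 6.3. It is the only planned between-arm test of instillation sensations, since the individual sensations are only described. If the patients who lose their total are the ones with sensations, those left in the test are mostly zeros in both arms, and a real difference between two differently formulated products would tend not to show.

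**Working it through.** The plan states no figure for this score, so there is none to reproduce. The check compares the rules and then traces patients through them.

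**Step 1. The two scores in SAP 3.3.**

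| | Dry-eye total | Instillation total |
|---|---|---|
| Items required | 7 | 6 |
| When zeros are created | for each item without a line | all six together, only if nothing was felt |
| Total if an item is missing | not derived | not derived |
| Patient with lines for two items only | other five become 0; scored | other four stay absent; no total |

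The SAP 6.8.1 note does not close the gap. It covers a patient who felt nothing and a severity already recorded as 0, but not an item without a record.

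**Step 2. The item lists.**

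| Item | Named for instillation (Protocol 6.3.3, 6.8.1.2.8; SAP 3.2) | Summed in SCORE_UPON | Dry-eye seven |
|---|---|---|---|
| Burning | yes | yes | yes |
| Stinging | yes | yes | yes |
| Itching | yes | yes | yes |
| Dryness | yes | yes | yes |
| Foreign body | yes | yes | yes |
| Light sensitivity | yes | **no** | yes |
| Fluctuating blurred vision | **no** | yes | yes |

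Both six-item lists are the dry-eye seven less one item, but a different item is left out of each.

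**Step 3. Trace by patient type.**

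1. Nothing felt: six zeros, total 0, always in the test.
2. Something felt, all six SCORE_UPON items graded including absent: total available.
3. Something felt, only felt items stored: total missing unless all six were felt.
4. Something felt, table fully completed with the items that the protocol and SAP 3.2 name: no predefined line for blurred vision, so the total is missing for every such patient.

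**Step 4. Illustration of size. All rates are assumptions.** The documents give no symptom rates. SAP 5.1 gives 101 randomised at 1:1, so take n = 50 per arm. Let p be the share of patients with any sensation and q the chance that a symptomatic patient has a given item (one item assigned at random if none is drawn). Severities 1/2/3 have probabilities 0.6/0.3/0.1, mean 0.6 + 0.6 + 0.3 = 1.5.

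- Mean total of a symptomatic patient: m = 1.5 × [6q + (1 − q)^6]. At q = 0.25: 1.5 × (1.5 + 0.178) = 2.517.
- Let c be the share of symptomatic patients who keep a total, unrelated to their score. The arm mean among scored patients is p·c·m / (1 − p + p·c), and the number lost over both arms is 50 × (p1 + p2) × (1 − c).

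With p = 30% v 10% and q = 0.25:

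| c | Arm means | Difference | Lost of 100 |
|---|---|---|---|
| 1 (type 2) | 0.755 v 0.252 | 0.50 | 0 |
| 0.5 | 0.378/0.85 = 0.444 v 0.126/0.95 = 0.132 | 0.31 | 10 |
| 0 (type 4) | 0 v 0 | 0 | 20 |

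For type 3, the share of symptomatic patients with all six items is q^6 / [1 − (1 − q)^6]: 0.03% at q = 0.25, 1.6% at 0.5 and 18% at 0.75. A simulation of type 3 (1,500 trials per setting, two-sided 5% Mann-Whitney) gave, at 30% v 10% and q = 0.25, means of 0.75 v 0.25 and power of about 71% with zero-filling. Without it, means were about 0.00 in both arms, power about 0%, and about 20 of 100 patients were lost. From 20% v 10% to 50% v 20%, with q = 0.25 or 0.5, about 15 to 35 of 100 patients were lost and power fell from 26–87% to 0–1%.

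**The case against.** The best defence of the plan is that the e-CRF probably supplies the zeros. Protocol 6.8.1.2.8 requires the table to be completed after a yes, on a scale that includes absent. The SAP 6.8.1 note speaks of a severity equal to 0, which presupposes recorded absent lines. SAP 3.3 also maps a stored absent value to 0. On that reading the rules fit together: a no leaves no lines, so six zeros are created; a yes leaves a graded table, which is summed. The illustration cannot contradict this, because its near-zero differences follow directly from assuming that only felt items are stored.

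This stands to the extent that loss through partial reporting is possible, not shown. It does not settle the matter, for two reasons. The dry-eye items have the same absent grade and no opening question, yet the SAP still provides for lines that do not exist; an absent grade on the scale therefore does not guarantee a stored line. And a fully completed table does not help if blurred vision is not on it.

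It is also fair to say that a loss would not be silent: SAP 5.2 and the table templates show missing counts by arm. But those counts do not show that the missing patients are the symptomatic ones. Double programming (SAP 10.1) would not reveal it either, since both programmers would apply the same rule.

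A last objection is that unconditional zero-filling would turn lines left blank by mistake into sensations not felt. That is right, and the fix allows for it.

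**Conclusion.** The derivation is incomplete and its item list disagrees with the items named for collection; both should be put right before lock. If the e-CRF stores only felt sensations, or holds the items that the protocol and SAP 3.2 name, symptomatic patients selectively lose their total and the Table 6.3 comparison is pulled toward no difference. If a yes always produces grades for the six SCORE_UPON items, nobody is lost through partial reporting. The e-CRF is not among the documents, so the size cannot be stated; the figures under the working show only how far it could go on assumed rates.

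A reader might infer that symptomatic patients will certainly drop out, or that the safety comparison as a whole is compromised. The documents support neither. The loss is conditional on the e-CRF, and it is confined to the total score. The per-sensation tables (6.1, 6.2), the tolerance ratings by patient and investigator (compared by CMH test) and the adverse event tables do not use SCORE_UPON. The primary non-inferiority analysis and the sample size are untouched.

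**What to change.** Amend SAP 3.3 before database lock.

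1. Align the six items in SCORE_UPON with those collected upon instillation in Protocol 6.3.3 and 6.8.1.2.8 and SAP 3.2, and check the list against the e-CRF. This has to come first: zero-filling on the present list could give a patient who reported only light sensitivity a total of 0.
2. Tie the score to the opening question:
   - answer no: total is 0;
   - answer yes with at least one sensation recorded, predefined or other: set predefined sensations that have no line to 0 and sum;
   - a line that is displayed but has no grade: leave it missing and query it;
   - answer missing, or yes with no line at all: total is missing.
3. Report by arm how many patients with a missing total answered yes. The templates already show missing counts; the split by answer is what is new.

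The cost is a few lines of derivation code and one extra table row, with no new data beyond any queries on blank grades. If the e-CRF already forces a grade on every item of the aligned list, the zero-fill rule changes no result.

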Secondary Performance criteria	
 • Change from baseline in total ocular staining grade according to Oxford grading scheme at Day 8 and Day 84 in the worst eye and at Day 8, Day 35 and Day 84 for contralateral eye. • Change from baseline in Van Bijsterveld score* (lissamine green staining) at Day 8, Day 35 and Day 84. • Change from Day1-10/Day1-7 (selection visit) in DEQ-5 at Day 35 and Day 84. • Change from baseline in OSDI (Ocular Surface Disease Index) score at Day 8, Day 35 and Day 84. • Change from baseline in Schirmer test result* (without anaesthesia) at Day 8, Day 35 and Day 84. • Change from baseline in TBUT* (Tear Break-Up Time) at Day 8, Day 35 and Day 84. • Conjunctival hyperaemia* using McMonnies photographic scale at Day 8, Day 35 and Day 84. • HLA-DR (AUF) at Day 84 in Right Eye if eligible eye. • Objective Scatter Index (OSI) at Day 35 and Day 84. • Dry Eye symptoms: burning/irritation, stinging/eye pain, itching, eye dryness feeling, foreign body sensation, light sensitivity and fluctuating blurred vision evaluated with a 4-level verbal scale (0 = Absent; 1 = Mild, Present but not disturbing; 2 = Moderate, Disturbing, but not limiting daily activities; 3 = Severe, Very distressing and interfering with daily activities) and change from baseline in total score of Dry Eye symptoms at Day 8, Day 35 and Day 84.

	
 Performance assessment by the investigator (Unsatisfactory, Not very satisfactory, Satisfactory, Very satisfactory) at Day 35 and Day 84. 
*Assessment recorded for each eye will be analysed for the worst eye and the contralateral eye.

Safety parameters	
 Ocular symptoms upon instillation at Day 8, Day 35 and Day 84: burning/irritation, stinging/eye pain, itching, eye dryness feeling, foreign body sensation, light sensitivity and other symptoms evaluated with a 4-level verbal scale (0=Absent, 1=Present but not disturbing, 2=Disturbing but not limiting daily activities, 3=Very distressing and interfering with daily activities). Far best-corrected visual acuity (in logMAR) at Day 84. Tolerance assessment by the patient and the investigator using a 4-point verbal scale (Unsatisfactory, Not very satisfactory, Satisfactory, Very satisfactory) at Day 35 and Day 84. Ocular and systemic adverse events (AE/SAE).

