6.3.3 Safety endpoints

Other evaluation parameters are:

- Ocular symptoms upon instillation at Day 8, Day 35 and Day 84: Burning/irritation, stinging/eye pain, itching, eye dryness feeling, foreign body sensation, light sensitivity and other symptoms will be graded by the subject according to the

following severity scale and with their duration: (0 = Absent; 1 = Mild, Present but not disturbing; 2 = Moderate, Disturbing, but not limiting daily activities; 3 = Severe, Very distressing and interfering with daily activities);

- Far best-corrected visual acuity (in logMAR) at Day 84;
- Tolerance assessment by the patient and the investigator (Unsatisfactory, Not very satisfactory, Satisfactory, Very satisfactory) at Day 35 and Day 84 ;
- Ocular and systemic adverse events (ADE/SADE).

These endpoints have been chosen considering the clinical literature review of Thealoz Duo® (Pinto-Bonilla et al. 2015; Schmidl et al. 2015; Schmidl et al. 2016-abstract; Chiambaretta et al. 2017). They are clinically relevant, clearly defined and assessed at a specified time point in order to provide clinical evidence on the performance and tolerance of the T2259 device in the target population for the management of the ocular signs and symptoms of patients with dry eye disease.

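### The instillation score in SAP 3.3 counts blurred vision in place of light sensitivity, against every definition of the endpoint and with no declared change

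*SAP*

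**What the plan says.** **Endpoint definitions.** SAP 3.2 states: "Burning/irritation, stinging/eye pain, itching, eye dryness feeling, foreign body sensation, light sensitivity and other symptoms will be graded by the subject". The protocol agrees in three places: the synopsis ("foreign body sensation, light sensitivity and other symptoms evaluated with a 4-level verbal scale"), section 6.3.3 ("foreign body sensation, light sensitivity and other symptoms will be graded by the subject according to the") and the collection procedure in 6.8.1.2.8 ("light sensitivity and other symptoms will be graded by the subject according to the following severity scale and with their duration"). Each gives six named symptoms plus an open category.

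**Scoring rule.** SAP 3.3 gives a different six: "The 6 predefined dry eye symptoms are: Burning/Irritation, Stinging/Eye pain, Itching, Eye dryness feeling, Foreign body sensation and Fluctuating blurred vision". The score is computed only "if the 6 predefined dry eye symptoms are not missing". For a patient with no symptoms upon instillation at a visit, "6 lines will be created for the 6 predefined symptoms, with CESEVn=0".

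**Fill-in rule for single items.** The neighbouring rule in SAP 3.3, for a visit where the "patient does not have all symptoms, missing symptoms will be created with CESEVn=0", is restricted to the general dry eye symptoms category. It does not cover the instillation category.

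**Use of the score.** SAP 6.8.1 compares it between groups by t-test, or by a Mann-Whitney Wilcoxon test if the data are not normal. SAP 4.3 records this change from the protocol's ANCOVA and refers to six symptoms, but it does not say that an item was replaced. Protocol 7.3.4 speaks of seven predefined symptoms and does not list them.

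**The concern.** A summed score should contain the items that define its endpoint. Here the derivation and the definition differ in one of six items, within the SAP as well as between SAP and protocol, and no reason is given.

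The score carries a between-group test, and SAP 10.1 places the instillation sensations at the critical validation level. Double programming does not by itself catch the fault, because both programmers work from the same item list.

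The substitution need not be neutral between arms. The Vismed Multi leaflet (protocol Appendix II) names momentary blurred vision among its rare effects; the T2259 leaflet (Appendix I) names only mild irritation and hyperaemia. This does not suggest intent, but it is a reason to settle the item list before unblinding.

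**Working it through.** The plan gives no figure to reproduce here, so the check is a comparison of lists followed by simple scoring.

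**1. Lists side by side**

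| Symptom | Protocol synopsis, 6.3.3, 6.8.1.2.8; SAP 3.2 (upon instillation) | SAP 3.3, SCORE_UPON | SAP 3.3, dry eye score |
|---|---|---|---|
| Burning/irritation | yes | yes | yes |
| Stinging/eye pain | yes | yes | yes |
| Itching | yes | yes | yes |
| Dryness | yes | yes | yes |
| Foreign body sensation | yes | yes | yes |
| Light sensitivity | yes | **no** | yes |
| Fluctuating blurred vision | **no** | yes | yes |
| Named items | 6 (plus other) | 6 | 7 |

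Five of six items are common. The SCORE_UPON list equals the seven-item dry eye list with light sensitivity removed, and it is still labelled as dry eye symptoms. A copying slip is the likeliest origin, although the documents do not establish it.

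**2. Effect on one patient.** Each item is graded 0 to 3, so six items give a maximum of 6 × 3 = 18. Take a patient with light sensitivity 3 and nothing else. The endpoint list gives 0 + 0 + 0 + 0 + 0 + 3 = 3. Under SAP 3.3 the result depends on the e-CRF:

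- The e-CRF has a blurred-vision row. The score is complete (0 to 18), and this patient scores 0. In general the score shifts by blurred vision minus light sensitivity, from 0 − 3 = −3 to 3 − 0 = +3.
- It has no such row, and the absent item is counted as 0. The score sums five collected items, with maximum 5 × 3 = 15. This patient scores 0.
- It has no such row, and the all-six condition is applied literally. This patient has no score.

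**3. Do the other rules rescue the third case?** Zero lines are created only for patients without symptoms upon instillation, and the item-level fill-in does not apply to this category. The note in SAP 6.8.1 sets severity to 0 when no sensation was felt or severity is absent. Read per patient, it does not help a symptomatic patient; read per item, it leads to the second case. Blurred vision written under the open category could give a score only to those who report it. Symptomatic patients may therefore be unscored in this case, but not necessarily all of them.

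**4. Secondary check, DEQ-5 total (SAP 3.3).** Four items are tested as `Ne .` (not missing), while the watery-eyes item is printed as `DEQ503n Ne 1`. Protocol 6.8.1.2.2 scores that item 0 to 4, with 1 meaning Rarely, and totals all five items by plain sum.

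- Possible complete answer patterns: 5 × 6 × 5 × 6 × 5 = 4500.
- Patterns with watery eyes = 1: 5 × 6 × 5 × 6 = 900, none of which gets a total under the printed rule.
- Example: answers 3, 3, 3, 3, 1 total 13 in the protocol and are unscored in the SAP as printed.

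These are counts of patterns, not of patients. Because the DEQ-5 baseline is the selection visit, an answer of 1 there would remove both the Day 35 and the Day 84 change.

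**The case against.** The strongest reply is that this is a labelling slip. If the e-CRF carries the six rows named in protocol 6.8.1.2.8, and the programmer sums the rows recorded in the instillation category, the intended 0 to 18 score results. SAP 10.1 also sets a default check in which a second person verifies the outputs against the CRF and the SAP, and that check is well placed to expose a wrong item name. Tables 6.1 and 6.2 report each sensation separately, so a missing symptom or a loss of scores would probably be noticed. All of this stands and lowers the likelihood of harm. It does not correct the text: the intended score would be obtained only by departing from the SAP.

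A reader might go further and infer that the instillation comparison collapses to zeros because every symptomatic patient loses the score. The documents do not support that. It needs an e-CRF without a blurred-vision row, literal programming, no use of the open category for blurred vision and no detection at output review.

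A reader might also infer that the DEQ-5 endpoint is certain to lose many patients. That is not supported either. The odd character stands in a table with other visible slips (one OSDI subtotal shows a stray `n` where the second item belongs), so it may be a text-reading artefact. The documents give no share of patients answering 1, so any percentage lost would be an assumption.

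**Conclusion.** The mismatch is established from the text alone: SCORE_UPON, as specified, is not the sum of the symptoms that define its endpoint, and SAP 4.3 does not declare the difference. With the rule followed as written, severe light sensitivity as the only sensation yields 0 or no score instead of 3.

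Whether a score is merely altered or is missing rests on e-CRF version MSC003, which cannot be seen here. No effect on the group comparison can be calculated from the documents. The DEQ-5 line is a point to verify, not an established error.

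The reach is one tested safety score and possibly one secondary performance endpoint. The tables for each sensation and each DEQ-5 item remain, and the primary analysis, its sample size and its error rate are untouched.

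**What to change.** Before database lock:

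1. Check which items e-CRF MSC003 collects for sensations upon instillation.
2. In SAP 3.3, replace fluctuating blurred vision by light sensitivity in SCORE_UPON, so that it matches SAP 3.2. If blurred vision is collected and its use is intended, declare and justify the item change in SAP 4.3 instead.
3. In either case, record in SAP 4.3 that the seven predefined symptoms of protocol 7.3.4 become six, and name them.
4. Look up the DEQ-5 condition in the original SAP. If `DEQ503n Ne 1` is confirmed, change it to `DEQ503n Ne .`; if it is a reading artefact, leave it.

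The cost is two look-ups, at most two derivation lines and one entry in SAP 4.3. No new data are needed.
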